6.2.5 Azacitidine Dose Adjustments

Azacitidine dose modifications will follow the Prescribing Information^{30,31} or institutional practice, supported by international recommendations. Azacitidine should be administered SC or IV over 7 consecutive days, Days **4-10**, every 28 days. A single missed dose (for any reason but toxicity) may, at the Investigator's decision, be compensated by adding an additional dosing day for azacitidine (e.g. Day **11**) so that the patient receives the total 7 days of treatment per cycle. If the azacitidine dose interruption is > 2 days, discuss with the Medical Monitor.

6.3 Concomitant Treatment

If patients experience prolonged myelosuppression they will be placed on infection prophylaxis per standard of care.

Patients may not receive any other drug to treat MDS while on study. Patients may continue their baseline medication(s) as long as they are not prohibited. Palliative and supportive care (e.g., anti-emetics, bisphosphonates) for disease related symptoms will be offered to all patients in the study per institutional practices. Adverse events will be treated

as clinically indicated. All concomitant medications that are currently in use or that become necessary during the study should be recorded.

Hydroxyurea may be administered before study start and up to the time of study randomization. At the investigator's discretion, for patients with significant leukocytosis during the early treatment cycles, hydroxyurea may be administered. The hydroxyurea should be discontinued as soon as clinically appropriate.

If the patient develops an acute infusion reaction (\geq Grade 2), the infusion must be stopped until the reaction is resolved to \leq Grade 1. Premedication (e.g., dexamethasone) may be used after the first cycle.

The prophylactic use of G-CSF is prohibited. Supportive use of G-CSF for treatment of cytopenias may be allowed at the discretion of the investigator per institutional practices.

6.4 Monitoring Subject Compliance

All instances of protocol deviations will be entered into Monitor Express and will be reviewed by the Investigator, Sponsor and appropriate Theradex designee.

Footnotes to Schedule of Study Evaluations

- a. All screening/baseline evaluations will be performed within 28 days prior to the start of APR-246 and azacitidine treatment. In the event that a visit or test cannot be scheduled on the exact visit day, a window of ± 3 days is allowable.
- b. A window of ± 3 days applies to this study visit.
- c. After the first cycle, Day 1 evaluations of subsequent cycles are to be done within 3 days prior to next cycle drug administration.
- d. Confirmation of TP53 status for eligibility will be performed centrally using the local lab report.
- e. Full medical history will be obtained at baseline for safety and eligibility purposes; this will include any issues/clinically significant findings from 28 days prior to screening date.
- f. Physical exam and vital signs (including blood pressure, heart rate, respiration rate and temperature) will be completed for safety purposes and clinically significant items will be recorded as AEs where appropriate. **In Experimental Arm, vital signs will be collected prior to APR-246, 2 hours into infusion and at end of infusion (EOI) (± 30 min. at all time points). Both arms: if azacitidine is given via IV infusion, vital signs will be taken before the infusion (within 0-2 hours) and at EOI (30-60 minutes); if azacitidine is given via SQ injection, vital signs will be taken before the injection (within 0-2 hours). In the Control Arm, the physical exam and vital signs are not needed on each day prior to the first day of azacitidine administration; vital signs will be assessed on treatment days only.**
- g. For Experimental Arm Only, APR-246 is administered IV on days 1-4 of each 28-day cycle.
- h. Azacitidine is administered SC over 7 consecutive days, on Days **4-10** of each 28-day cycle. On **Day 4** azacitidine is administered immediately after the APR-246 infusion. SC route is preferred but site may give IV at the investigator's discretion. The same route should be maintained over the 7-day treatment period (whichever route is used on day **4**, the other days should follow the same route of administration).
- i. **Bone marrow aspirate sample and biopsy core is collected at baseline and when bone marrow is sampled for disease assessment. If no aspirate is available, then peripheral blood is acceptable. Bone marrow assessment completed within 28 days of signing consent will be accepted to fulfill screening requirement, as long as it has been completed following the last MDS treatment (excluding ESAs (erythropoietic stimulating agent)).**
- j. Hematology including hemoglobin, hematocrit, MCV, platelet count, blasts, WBC and WBC differentials weekly. **The peripheral blood sample collected on Day 1 of each cycle starting at Cycle 2 will be for disease assessment, if bone marrow aspirate is not available (see footnote r).** For patients with documented CR at disease assessment following Cycle 2, hematology and blood chemistry assessments will be required for D1 of each subsequent cycle and more frequently per the discretion of the treating physician. Otherwise performed weekly until CR.

- k. Blood chemistry including sodium, potassium, BUN, glucose, ALT/AST, alkaline phosphatase, total protein, total bilirubin, albumin, creatinine, calcium, chloride and magnesium weekly. At screening, the creatinine clearance may be calculated from the serum creatinine. A 24-hour urine for Creatinine Clearance may be performed at investigator's discretion. For patients with documented CR at disease assessment following Cycle 2, hematology and blood chemistry assessments will be required for D1 of each subsequent cycle and more frequently per the discretion of the treating physician. Otherwise perform weekly until CR.
- l. Pregnancy test; for women of childbearing potential, a negative pregnancy test (urine or serum) must be documented between Screening and first day of treatment on study. Must be documented prior to 1st dose of treatment on study.
- m. Standard 12-lead ECGs to be performed in triplicate at baseline/screening, on Days 1 - 4 of Cycle 1 (experimental arm only) and on Days 1 of each subsequent cycle (experimental arm only) with patient in a semi-recumbent position. Please consult Table 10 for ECG collection schedule.
- n. Please consult section 8.3, Table 9 for PK collection schedule.
- o. Patients discontinuing treatment early should complete their end of treatment visit within approximately 28 days of their last dose of investigational product. Physical exam, vital signs, adverse event reporting, CBC (complete blood count), and blood chemistry and BM aspirate and biopsy with NGS analysis should be performed if feasible.
Off Treatment assessment includes best response, date of first response, date of loss of response, reason for discontinuation.
Off study CRF: vital status, date of death/last contact, transformation to AML and the date of transformation to AML if applicable.
- p. Long-term follow up can be done remotely (e.g. via telephone, via Local Practitioner or via review of medical records). Assuming there is no withdrawal of consent, patients who stop study treatment (APR-246 or azacitidine) for any reason (e.g. toxicity, transition to SCT, PD) will continue long-term follow-up (see Section 7.6).
If a patient is removed from the study due to unacceptable adverse events, the event(s) will be followed until resolution or stabilization of the adverse event.
- q. AE description, grade and start date and resolution date should be captured and documented.
- r. Response assessment is performed at the end of each cycle (every 4 weeks), based on peripheral blood and bone marrow (at the end of even cycles), and peripheral blood alone (at the end of odd cycles).

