During subsequent cycles ECG should be collected in triplicate prior to infusion of APR-246 on Day 1 of each cycle. QTcF must be calculated from a mean of all three ECG readings to confirm it does not exceed 449 msec. If pre-dose QTcF is 450-469 msec, APR-246 may be administered, and additional triplicate ECG should be performed at the end of infusion (6 hours after start of infusion, ± 30 min). If post-dose ECG shows a significant change in QTcF, defined as either: a) increase > 60 msec from baseline (or pre-dose), or b) increase to an absolute value ≥ 501 msec, i.e. consistent with NCI CTCAE Grade 3 QTc prolongation, QTc prolongation must be confirmed by a manual assessment of the ECG, and using Fridericia's correction ($QTcF = QT/RR^{0.33}$). If confirmed, the therapy should be interrupted until a cause

(electrolyte disorders or an effect of a concomitant medication) has been identified and addressed, and QTcF has returned to < 470 msec. If all other causes for clinically significant QT interval prolongation are excluded, APR-246 must be permanently discontinued. If QTcF is unchanged or there is no significant change, additional ECG is not required during that cycle.

If repeated QTcF measurements show a stable QTcF < 450 msec, or if QTcF remains stable within the interval of 450 – 469 msec with no significant change at the end of infusion during several cycles of treatment, reducing the number of ECGs performed in the study may be discussed with the Medical Monitor.

If a patient starts treatment with another medication known to prolong QT interval at any time during the study therapy, an additional pre- and post-dose (6 hours after start of infusion, ± 30 min) ECG should be performed on the next treatment day. For patients who do not tolerate the protocol-specified dosing schedule, one dose level reduction is permitted (Table 5) in order to allow the patient to continue the study treatment. A second dose reduction could be permitted following discussion with the Sponsor and Medical Monitor.

Table 5. APR-246 Dose Levels

Dose Modification	APR-246 Dose
Starting Dose Level (DL)	APR-246 4.5 g/day 1.5 g (for first 45 minutes) + 3.0 g (for 5 hours 15 minutes)
One dose level reduction (DL-1)	APR-246 4.0 g/day 1.33 g (for first 45 minutes) + 2.67 g (for 5 hours 15 minutes)
Second dose level reduction (DL-2)*	APR-246 3.5 g/day 1.16 g (for first 45 minutes) + 2.34 g (for 5 hours 15 minutes)

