7.2.1 Screening (All patients)

All pre-treatment evaluations are to be performed within 28 days of Day 1 unless otherwise noted.

- Informed Consent
- TP53 mutation confirmation – send local report to vendor (see lab manual for instructions)
- Medical history – must include a thorough assessment and documentation of all transfusions received beginning from 8 weeks prior to randomization to end of treatment/off treatment; record transfusions on transfusion log.
- Physical examination
- Height
- Weight
- ECOG performance status
- Creatinine clearance (Cockcroft-Gault method; see [Appendix IV](#))
- Vital signs: including blood pressure, heart rate, respiration rate and temperature
- Hematology: hemoglobin, hematocrit, MCV, platelet count, blasts, WBC and WBC differentials.
- Blood chemistry including sodium, potassium, BUN, glucose, ALT/AST, alkaline phosphatase, total protein, total bilirubin, albumin, creatinine, calcium, chloride and magnesium.
- Serum pregnancy test: For patients with reproductive potential.
- ECG: Standard 12-lead ECGs to be performed with patient in a semi-recumbent position in triplicate.
- Concomitant medication
- Bone marrow aspirate and biopsy - Bone marrow assessment completed within 28 days of signing consent will be accepted to fulfill screening requirement as long as it has been completed following the last MDS treatment (excluding ESAs).
- Baseline bone marrow aspirate and biopsy core for exploratory objectives. If no aspirate is available, then peripheral blood is acceptable.
- Adverse Events: baseline, at the time of eligibility confirmation.

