8.1.1 Safety Analysis

Safety data including AEs, vital signs, laboratory data, ECG, and physical exam will be tabulated for the safety population. Adverse events will be tabulated by body system, preferred term, severity, and relationship to treatments. The tabulation of laboratory parameters will include the normal ranges for each parameter. Each value will be classified as falling above, below, or within the normal range. Laboratory parameters will also be tabulated by maximum NCI-CTCAE severity grade.

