8.1.2 Reporting of Adverse Events

8.1.2.1 Adverse Events

An adverse event (AE) is any untoward medical occurrence in a patient or clinical investigation subject administered a pharmaceutical product that does not necessarily have a causal relationship with the treatment. An adverse event includes abnormal laboratory values or test results, even when they do not induce clinical signs or symptoms or require therapy.

The adverse event reporting period begins at the time of eligibility confirmation and will continue up to 30 days after the last dose of study treatment.

At each evaluation patients should be interviewed in a non-directed manner to elicit potential adverse reactions from the patient. The occurrence of an adverse event will be based on changes in the patient's physical examination, laboratory results, and/or signs and symptoms.

All adverse events (except Grade 1 and 2 laboratory abnormalities that do not require an intervention), regardless of causal relationship, are to be recorded in the case report form and source documentation. Adverse events are to be coded according to MedDRA version 21.1. The Investigator must determine the intensity of any adverse events according to the NCI Common Terminology Criteria for Adverse Events (CTCAE) Version 5.0 (see

<http://ctep.info.nih.gov>) and their causal relationship. Those AEs not covered by these criteria will be graded as follows:

1. Mild: Discomfort noticed, but no disruption of normal daily activity. Prescription drug not ordinarily needed for relief of symptom but may be given because of personality of patient.
2. Moderate: Discomfort sufficient to reduce or affect normal daily activity. Patient is able to continue in study; treatment for symptom may be needed.
3. Severe: Incapacitating, severe discomfort with inability to work or to perform normal daily activity. Severity may cause cessation of treatment with test drug; treatment for symptom may be given and/or patient hospitalized.
4. Life-Threatening: Symptom(s) place the patient at immediate risk of death from the reaction as it occurred; it does not include a reaction that, had it occurred in a more serious form, might have caused death.
5. Fatal: Event caused the death of the patient.

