8.4 ECG in Experimental Arm: ECG for APR-246

Table 10 describes the routine ECG requirements from screening through cycle 4:

Table 10. ECG Requirements in Experimental Arm

Time Point	ECG, number	Timing
Baseline/Screening	Triplicate	Must be within 28 days of C1D1
Cycle 1, Days 1-4	Triplicate	Pre-dose; Post dose (6 hrs. after start of infusion; ± 30 min)
Cycles 2+, Day 1	Triplicate	Pre-dose

If repeated QTcF measurements show a stable QTcF < 450 msec, or if QTcF remains stable within the interval of 450 – 469 msec with no significant change at the end of infusion during several cycles of treatment, reducing the number of ECGs performed in the study may be discussed with the Medical Monitor.

If a patient starts treatment with another medication known to prolong QT interval at any time during the study therapy, an additional pre- and post-dose (6 hours after start of infusion, ± 30 min) ECG should be performed on the next treatment day.

Please consult Section 6.2.1 for additional requirements for proceeding with treatment with APR-246.

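### Protocol-scheduled on-study ECGs are done in the experimental arm only, so low-grade ECG and QTc adverse events are unequally detected in the two-arm safety tables.

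*Combined protocol and SAP*

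**What the plan says.** **Collection.** All patients have a screening ECG (Section 7.2.1: "ECG: Standard 12-lead ECGs to be performed with patient in a semi-recumbent position in triplicate"). After that, footnote m to the Schedule of Study Evaluations places ECGs "on Days 1 - 4 of Cycle 1 (experimental arm only) and on Days 1 of each subsequent cycle (experimental arm only"). Tables 4 and 10 give the timing. On Cycle 1 Days 1 to 4 there is a pre-dose triplicate and a second one described as "Post dose (6 hrs. after start of infusion; ± 30 min"). From Cycle 2 there is one pre-dose triplicate on Day 1 (Section 6.2.1: "During subsequent cycles ECG should be collected in triplicate prior to infusion of APR-246 on Day 1 of each cycle"). The control-arm visit lists (Section 7.4) and the end-of-treatment visit (Section 7.5) contain no ECG.

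**Later post-dose ECGs are conditional.** Section 6.2.1: "If pre-dose QTcF is 450-469 msec, APR-246 may be administered, and additional triplicate ECG should be performed at the end of infusion". Starting a QT-prolonging drug triggers "an additional pre- and post-dose (6 hours after start of infusion, ± 30 min) ECG should be performed on the next treatment day" (Section 8.4), and Section 6.2.3 requires ECG monitoring around the infusion in patients given such drugs. The number of ECGs may be reduced after discussion with the Medical Monitor when QTcF is stable (Sections 6.2.1 and 8.4).

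**Analysis.** Section 8.1.1: "Safety data including AEs, vital signs, laboratory data, ECG, and physical exam will be tabulated for the safety population". Section 9.2 admits to that population anyone given a dose of either drug. The synopsis lists ECGs among the safety endpoints, and Section 3.2 sets the safety profile as an objective measured against azacitidine alone. Section 8.1.2.1: "An adverse event includes abnormal laboratory values or test results, even when they do not induce clinical signs or symptoms". Section 9.3.3 names adverse events and laboratory parameters and gives no method for ECG or QTc.

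**The concern.** An asymptomatic QTc prolongation is found only if someone records an ECG. One arm has a dense schedule of them and the other has none after baseline. When the resulting events go into a two-arm table by preferred term, the difference between columns mixes any drug effect with the difference in looking, and nothing in the table tells the reader how much is which.

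Section 2.8.1 names QTc prolongation as a potential risk of APR-246, so these rows will be read closely. Such events also count towards the number of patients with any adverse event, which feeds the overall tolerability comparison. No passage restricts ECG summaries to one arm or acknowledges the unequal detection. Section 8.1.2.1 exempts minor (Grade 1 and 2) laboratory abnormalities needing no intervention from recording, but gives no matching exemption for minor ECG findings.

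**Working it through.** The plan gives no expected QTc event rate, so there is no figure of its own to reproduce. The count in step 1 needs no assumption. Steps 2 to 4 are illustrations with assumed inputs, because the Cardiac Safety Overview (Section 2.6.6) is redacted in the public copy.

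**1. Scheduled on-study time points** (footnote m, Tables 4 and 10, Section 7.4)

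- Experimental, Cycle 1: 4 days × 2 (pre-dose and post-dose) = 8 time points, or 8 × 3 = 24 tracings.
- Experimental, each later cycle: 1 time point, 3 tracings. Over six cycles: 8 + 5 = 13 time points.
- Control: 0 in every cycle.

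**2. Simple detection model, no drug effect.** Let q be the assumed chance that one time point is flagged, equal in both arms, and treat time points as independent. The chance of at least one flag in k looks is 1 − (1 − q)^k. Section 9.3.3 counts only events from the start of the Cycle 1 Day 1 infusion, so the Day 1 pre-dose ECG drops out and 7 treatment-emergent looks remain in Cycle 1.

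| q (assumed) | 8 looks | 7 looks | 13 looks | Control, 0 looks |
|---|---|---|---|---|
| 0.2% | 1.6% | 1.4% | 2.6% | 0% |
| 1% | 7.7% | 6.8% | 12.3% | 0% |
| 5% | 33.7% | 30.2% | 48.7% | 0% |

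Example: 1 − 0.99^7 = 0.068, or about 5 of the 77 patients per arm in Section 9.1. With equal schedules the two columns would agree at any q.

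**3. Threshold illustration, no drug effect.** Assumed inputs: patient mean QTcF normal with mean 425 and SD 18 msec; visit-level SD of the triplicate mean 8, 10 or 12 msec; patients kept if screening QTcF is below 470 msec. Count as new a patient below 450 msec both at screening and at Cycle 1 Day 1 pre-dose who then has at least one of the remaining 7 Cycle 1 readings at 450 msec or more. By simulation, as a share of all experimental patients:

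- SD 8: about 10% (0.099 × 77 = 7.6 patients).
- SD 10: about 13% (0.134 × 77 = 10.3).
- SD 12: about 17% (0.170 × 77 = 13.1).

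Scheduled ECGs in control would find none. The 450 msec line stands in for a low-grade finding. The protocol does not define it as an adverse event; Section 6.2.1 uses it only to trigger an extra ECG in later cycles.

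**4. Severe findings.** Section 6.2.1 defines a significant change as a rise of more than 60 msec or a value of 501 msec or more, and ties the latter to Grade 3. In the same model, measuring the rise from screening, about 0.02% of patients meet this at SD 10 and about 0.2% at SD 12. The larger figure is 0.002 × 77 = 0.15 of a patient.

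**The case against.** The strongest reply is that this is openly labelled, drug-specific monitoring. The plan sets no between-arm ECG test, control has no scheduled post-baseline ECG data to tabulate, and the primary endpoint and power are unaffected. That is fair as regards severity, and the monitoring itself is not in question. It does not answer the point about the adverse event tables, where an event found by a scheduled ECG appears under its preferred term with no mark of how it was found.

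Several stronger readings are tempting, and the documents do not support them.

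- **That the tables will make QTc risk seem to fall after Cycle 1.** No by-cycle ECG table is planned; summaries at scheduled time points are specified for laboratory parameters only. Nor does end-of-infusion sampling stop: it continues when triggered.
- **That about 27% of patients would be flagged by chance.** The step 3 model does give 27% with any of 8 readings at 450 msec or more at SD 10, against 10% for a single reading. But that 27% counts the Day 1 pre-dose ECG and patients already at 450 msec or more at screening, about 10% in the model. Neither is a new, treatment-emergent finding.
- **That control events must be zero.** Clinically indicated ECGs are not forbidden in control. The chance of detection differs; the control rate need not be nil.
- **That severe event counts are distorted.** Step 4 shows almost nothing at Grade 3 level.

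One uncertainty stands. Section 8.1.2.1 goes on to base the occurrence of an adverse event on physical examination, laboratory results, and signs or symptoms, without naming ECG. Sites may therefore differ in whether they record an isolated reading. This makes the size uncertain and does not remove the imbalance.

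**Conclusion.** The point holds as a detection bias in low-grade ECG and QTc adverse events and, through them, in any-AE counts. The schedule asymmetry is certain: 8 against 0 time points in Cycle 1, then 1 against 0 per cycle. Its effect on the tables depends on how often sites record minor ECG findings as adverse events. If every new reading of 450 msec or more were recorded, the assumed values give roughly 10 to 17% of experimental patients in Cycle 1 with no drug effect. That range rests on an assumed mean and SDs, independent visit-level error and a threshold that the protocol does not use as an event criterion. Grade 3 or higher counts are little affected, and the sample size and complete remission analysis not at all. It is worth correcting in the safety analysis text because the correction is cheap and QTc is a named risk.

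**What to change.** Amend Sections 8.1.1 and 9.3.3. No ECG is added or removed and no treatment rule changes.

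1. Summarise ECG and QTcF for the experimental arm only, as change from each patient's own baseline, with the number of patients and of ECGs at each time point. Show routine and triggered post-dose ECGs separately, so that readings from patients selected for higher QTcF or for co-medication are kept but not pooled with routine ones.
2. List asymptomatic ECG and QTc adverse events found by a protocol-scheduled ECG in a separate table. Show the between-arm any-AE comparison with and without them, and footnote that ascertainment differed by arm.
3. If a by-cycle QTcF display is made, state that Cycle 1 against later cycles is not a trend in risk: routine end-of-infusion sampling is confined to Cycle 1, and later sampling is triggered or may be reduced. Restricting the display to Day 1 pre-dose ECGs would not fully solve this, because those too may be thinned in patients with stable QTcF.

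Cost: SAP wording, one extra table, and some judgement in classifying how an event was detected. That classification rule should be fixed before the data are reviewed.
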